7.6 Missing data imputation

(ICH E3; 9.7.1, 11.4.2.2. ICH E9; 5.3. EMA Guideline on Missing Data in Confirmatory Clinical Trials)

Patients without quantitative biomarker values at the baseline visit will be assigned the mean of the patients at that visit. Patients without quantitative values at the follow-up visits will be assigned the same value as in the baseline visit. This imputation is intended to be conservative and go against the study objective (to detect a significant evolution between pre- and post-treatment biomarker values). In the case of qualitative variables, the lack of mutation or the characteristic analyzed will be assumed.

The different study populations where the different analyses will be performed will help to assess the imputation on the results. The analyses are only considered positive if the result is equivalent in all the analysis populations used.

7.7 Analysis of the specific effects of each site.

(ICH E3; 9.7.1, 11.4.2.4. ICH E9; 3.2)

The number of patients enrolled in each site will be described. Considering the small sample size, no analyses are expected to adjust the results by the site effect.

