7.2 Populations for analysis

(ICH E3; 9.7.1, 11.4.2.5. ICH E9; 5.2)

Full analysis set

This set will include all the patients who have received the treatment. This set will also be the safety analysis set.

Per protocol set

This set will include all the patients of the full analysis set that do not have major protocol violations that may affect the assessment of treatment in the primary variable (e.g., non-evaluable patients for

biomarkers). The definition of these deviations is described in section 9.1. For the analysis of secondary variables, the number of evaluable patients for a certain biomarker analysis set will be considered.

Sensitivity analysis

The primary biomarker analysis (significant inhibition of cyclin D1, Ki67 and active caspase-3) and the secondary analyses will be performed in the full analysis set and the per protocol population.

The safety analyses will be performed in the full analysis set.

PKD population

We propose to analyze and model pharmacokinetics (PK), pharmacokinetics-pharmacodynamic (PBMC) and AZD2281 concentration, considering all patients with a complete treatment concentration-time profile.

Analyses will not be repeated between different analysis populations if they only differ by 10% patients. The largest analysis population will be used for the analyses.

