7.8 Alpha error correction through multiple analyses

(ICH E3; 9.7.1, 11.4.2.5. ICH E9; 2.2.5)

The type-I error for primary biomarker analysis is 10%. As we analyze the inhibition of three biomarkers as primary variable (cyclin D1, Ki67 and active caspase 3), the type I error was divided into 3,3% (<5%) for each analysis.

Prior to the completion of the study, an interim analysis with a cut-off dated 08-May-2018 will be performed in case the study was not completed up to that date. The results will be presented at the ASCO annual meeting 2018. In order to correct the alpha error associated with multiple primary analyses, it was considered that only statistically significant biomarker differences could be declared when the analysis showed p-values <3.3% in the interim and the final analyses for both analysis populations (full analysis set and per protocol set).

For secondary analyses (analysis of the difference and correlation between the levels of different biomarkers), multiple analyses were corrected through Benjamini-Hochberg's procedure "false Discovery rate (FDR)" of 10%. This procedure lists the analyses performed from lowest to highest p-value. A difference is considered statistically relevant in an analysis if the p-value obtained is equal or lower than the range assigned in that analysis, divided into the number of analyses and multiplying by 10%.

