9 STATISTICAL REPORT SECTIONS

9.1 Summary of analysis.

This analysis will show the following tables and figures:

Figure 1. Patients enrolled and included in the study.

Table 1. Description of the analysis population. Descriptive statistics. All patients enrolled.

Table 2. Patient baseline characteristics. Descriptive statistics. Full analysis and per-protocol set.

Table 3. Patients who achieve a significant inhibition in the histological score between the post-treatment and pre-treatment period. Inferential statistics. Full analysis and per-protocol set.

Figure 2. Difference between the baseline and post-treatment levels of biomarkers (cyclin D1, Ki67, active caspase 3 and PARP1). Inferential statistics. Full analysis and per-protocol set.

Figure 3. Correlation between the levels of biomarkers with significant inhibition and PARP1. Inferential statistics. Full analysis and per-protocol set.

Figure 4. Change between baseline biomarker levels (PARP1 and with significant inhibition) depending on the mutation or deficiency identified (including MSI). Inferential statistics. Full analysis and per-protocol set.

Table 4. Adverse events observed in the study, occurred at least in 10% of patients. Descriptive statistics. Safety analysis.

Table 5.- Plasma concentrations of the drug for each patient by time.

Figure 5.- Mean plasma level curve of the drug by time.

9.2 Study full analysis.

9.2.1 Patients recruited, enrolled and disposition of patients in the study.

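### Imputing a missing baseline with the visit mean can create a responder with no observed change, and the SAP is inconsistent on whether its two-population check would catch it

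*SAP*

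**What the plan says.** **Imputation.** SAP 7.6 has two rules for quantitative biomarkers. For a missing baseline: "Patients without quantitative biomarker values at the baseline visit will be assigned the mean of the patients at that visit". For a missing follow-up value, the patient's own baseline is carried forward. The section then says: "This imputation is intended to be conservative and go against the study objective".

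**Response.** Under 5.4 a patient responds to a marker if the score falls by at least 50% and the log drop exceeds 1.6448 times the between-patient SD of the log baselines. A marker is declared inhibited if 5 of 36 patients respond. Dropouts count as non-responders.

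**Safeguard.** 7.8 allows a primary declaration only with p-values under 3.3% "in the interim and the final analyses for both analysis populations (full analysis set and per protocol set"). 7.6 has a looser form: "The analyses are only considered positive if the result is equivalent in all the analysis populations used". 7.2 says the primary analysis "will be performed in the full analysis set and the per protocol population", and Table 3 in section 9.1 is planned for both sets.

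**Text that cuts across the safeguard.** 7.2 also says: "Analyses will not be repeated between different analysis populations if they only differ by 10% patients"; the largest set is then used. 7.2 names patients who are non-evaluable for biomarkers as its example of per-protocol exclusion. The section 8 table instead answers No to per-protocol exclusion when the pre-treatment biopsy (MT1) was not collected, and Case by case for missing or non-evaluable pre- and post-treatment values.

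**The concern.** Carrying the baseline forward sets the change to zero, so that patient cannot respond. The visit mean has no such property. It gives an average starting point to someone whose marker may always have been low, and a genuine low post-treatment score then reads as a large fall. The dropout rule in 5.4 does not reach a patient who completed treatment and has a post-treatment score but no baseline. The sentence claiming conservatism may have been meant only for the carry-forward rule, but it follows both.

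7.6 also leaves open whether the mean is taken on the raw or log scale, and whether imputed values enter the baseline SD. The second point affects everyone: constants placed at the centre shrink the SD and lower the response threshold for all 36 patients.

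One created responder is one of the five needed. The two-population condition would deal with this only if the per-protocol analysis is actually run and the patient is out of it. The SAP contradicts itself on both.

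**Working it through.** **1. The plan's own figure.** With a 5% null rate (the one-sided 0.05 patient-level criterion), the exact binomial P(at least 5 of 36) is 3.24%, and three markers sum to 9.7%. This agrees with the stated 3.3% per marker and under 10% overall. Power at a 35% rate is 99.9% rather than the stated 95%; that is a separate matter. Five responders are still needed for p < 3.3% in a smaller set: P(at least 5) at n = 35, 34, 33 is 2.90%, 2.59%, 2.30%.

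**2. One patient (assumed values).** Visit mean 100, unseen true baseline 40, post-treatment score 40, log SD 0.5. The scored fall is 60%. The log drop is ln(100/40) = 0.916 against 1.6448 × 0.5 = 0.822. Both criteria are met, with no true change.

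**3. How often, for an unchanged marker.** Assume log-normal scores with log SD s, and let t = max(1.6448s, ln 2). An observed patient is never a responder. An imputed one is with probability:
- log-scale mean: Φ(−t/s)
- raw mean: Φ((s²/2 − t)/s)

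| log SD | log mean | raw mean |
|---|---|---|
| 0.3 | 1.0% | 1.5% |
| 0.7 | 5.0% | 9.8% |
| 1.0 | 5.0% | 12.6% |

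**4. Study level.** Simulation with 100,000 trials per setting: 36 patients, no drug effect, one look, log-normal pre/post scores, and 0-3 baselines replaced by the mean of the rest. The table shows P(at least 5 responders) per marker at pre/post correlation 0.5 and log SD 0.7-1.0.

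| Baselines missing | No effective check | Check runs and excludes these patients |
|---|---|---|
| 0 | 5.5-5.7% | – |
| 1 | 5.9-7.0% | 5.1-5.3% |
| 2 | 5.9-8.9% | 4.7-4.9% |
| 3 | 6.1-10.9% | 4.3-4.5% |

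The excess over 3.3% with nothing missing is a separate issue. The range with three missing and no check splits as follows:
- log mean, SD from observed baselines: about 6.1%
- raw mean, SD from observed baselines: 7.4-8.1%
- log mean, imputed values in the SD: about 9.0%
- raw mean, imputed values in the SD: 10.3-10.9%

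**5. Sensitivity.**
- Scores capped at 300 (assumed median 100), same settings: 6.6-8.0% with none missing; with three missing, 7.2-13.9% without the check and 5.1-6.5% with it.
- Correlation 0.7: at most 1.4% (2.4% capped).
- Correlation 0.5, log SD 0.4: from 1.2% to 1.3-1.8%. At log SD 0.3: about 0%.
- Correlation 0.3, log SD 0.7-1.0: 19.6-19.8% with none missing; with three missing, 19.0-19.2% (log mean, observed SD) or 26.9-27.6% (raw mean, imputed values in the SD).

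**6. Does the check apply?**
- *Exclusion.* On the section 8 row for MT1 not collected, the imputed patient stays in both sets, so agreement between them tests nothing. The missing-values row is decided case by case and, as worded, may not cover a baseline missing alone. 7.2's example points to exclusion.
- *Running it.* Read as 10% or less, the rule in 7.2 covers 1-3 patients of 36 (3/36 = 8.3%; 4/36 = 11.1%). With one set run, 7.6's requirement for the populations used is met trivially, while 7.8 still asks for both.

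**The case against.** There is a good case for treating this as minor.

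- **Rarity.** Inclusion criterion 1 requires a centrally checked biopsy with mandatory re-biopsy if tissue is inadequate, so a patient with no MT1 could hardly enrol. The realistic case is a marker that cannot be scored on a collected biopsy, which 7.2's example would exclude. This stands and limits the weight of the point. Even so, 7.6 and section 8 both provide for missing baselines.
- **The unchanged-marker contrast cannot by itself flip the trial.** With at most three imputed patients and no other responders, five cannot be reached. This is correct: step 3 shows the mechanism, and only step 4 speaks to the study result.
- **Most of the upper range comes from the SD.** With three missing, putting imputed values into the SD adds more than the created responder does, and using observed baselines is a natural reading of 5.4. A log mean with observed-only SD is close to neutral. This also stands, but the SAP does not choose among these readings.
- **7.8 is specific and the 10% rule general, so 7.8 should prevail.** This is a reasonable reading, but the SAP does not say so, and the MT1 row would still defeat the check.
- **One look.** If the interim takes place, 7.8 also requires success there, so the simulated rates are then upper bounds. This stands.

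**Conclusion.** The point holds, as a clarification and not a major flaw. The visit-mean rule does not deliver the conservatism that 7.6 claims: a patient with a post-treatment score and no baseline can enter the primary count as a responder whose change was never observed. The SAP's own safeguard would cure this, since there is no inflation when it runs and excludes these patients, but 7.2, 7.6, 7.8 and section 8 do not agree on whether it does.

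In the main setting (correlation 0.5, log SD 0.7-1.0, three baselines missing, no effective check), the false-declaration rate per marker rises from 5.5-5.7% to between 6.1% and 10.9%, depending on choices the SAP leaves open. The rise is negligible at higher correlation, at small SD, or with a log mean and observed-only SD. All sizes rest on assumed SD, correlation and missingness, so confidence in the magnitude is moderate. The conflict in the text does not depend on those assumptions.

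**What to change.** - **7.6:** for the primary response count in the full analysis set, treat a patient with no evaluable baseline for a marker as a non-responder for that marker, extending the dropout rule in 5.4. Compute the baseline SD from observed baselines only. If the visit mean is kept for other analyses, state its scale.
- **Section 8 and 7.2:** reconcile them so that such a patient leaves the per-protocol analysis of that marker only. Correct the reference in 7.2, which points to 9.1 although the deviation table is in section 8.
- **7.2:** state that the 10% rule does not apply to the primary count, so that the two-population condition in 7.8 is always checked.

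The cost is SAP wording, plus one more table when the sets are nearly equal. The response count falls slightly. With three baselines missing, power (exact binomial, at least 5 of 33 against at least 5 of 36) goes from 99.9% to 99.7% at the SAP's 35% rate, and from 87% to 82% at an assumed 20% rate.

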7 STATISTICAL METHODS

7.1 General considerations

The demographic and baseline numeric variables will be summarized by the number of patients, the number of valid patients, mean, standard deviation, median, quartiles, maximum and minimum. The frequency and percentages based on the total of patients in the analysis set will be reported for the categorical variables. Quantitative variables will be summarized by the number of patients, mean, median, 95% confidence interval, standard deviation, quartiles, minimum and maximum, as appropriate. Qualitative variables will be summarized by the frequency, the percentage and the confidence interval of the odds ratio, where appropriate.

Time-to-event variables will be summarized by showing the number of events, percentage, median survival with its 95% confidence interval, and will be analyzed through the Kaplan-Meyer method.

The evolution of quantitative variables will be analyzed through the Wilcoxon's non-parametric test, mean difference, medians and their 95% confidence intervals.

The evolution of qualitative variables will be analyzed through the McNemar test.

No inferential statistics will be performed for baseline variables or safety variables, unless otherwise specified.

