7.3 Covariate and subset analysis

(ICH E3; 9.7.1, 11.4.2.1. ICH E9; 5.7. CPMP 2002; 4. CPMP 2003.)

In the covariate and subset analysis, the pre-treatment and post-treatment biomarker levels and the differences between these two periods will be analyzed. For the subset analysis, biomarker levels will be compared through the Mann-Whitney U test. When comparing qualitative variables between different subsets, the Chi-square test or Fisher's exact test will be used. The correlation between different quantitative variables or discrete variables will be performed through Spearman's correlation, and their corresponding 95% confidence intervals will be presented. The subset analysis will include the difference of the biomarker level depending on the different molecular (p53, MSI, POLE...) and clinical (days since surgery, administration breach [>3 days, >6 days, ≥ 14 days]) classifications.

[figure not shown]

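### Setting missing follow-up biomarker values to baseline suits the responder count, but if applied to secondary change estimates, intervals and correlations of changes it biases them

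*SAP*

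**What the plan says.** SAP 7.6 covers every quantitative biomarker and makes no distinction between analyses. A patient with no follow-up value "will be assigned the same value as in the baseline visit". The SAP adds: "This imputation is intended to be conservative and go against the study objective", and explains in parentheses that the objective meant is detection of a pre/post change.

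The analyses that could receive these values are in three places:

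- **SAP 7.1:** "The evolution of quantitative variables will be analyzed through the Wilcoxon's non-parametric test", together with mean differences, medians and 95% confidence intervals. Handling of zero differences is not stated.
- **SAP 7.3:** correlation "will be performed through Spearman's correlation", with 95% intervals. The section includes pre/post differences among the quantities analysed.
- **SAP 7.8:** secondary differences and correlations go into a Benjamini-Hochberg procedure at a 10% false discovery rate.

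Two provisions limit the rule. SAP 7.6 says "The analyses are only considered positive if the result is equivalent in all the analysis populations used". SAP 7.2 says that for secondary variables "the number of evaluable patients for a certain biomarker analysis set will be considered".

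Two others loosen those limits. SAP 7.2 also runs the secondary analyses in both the full analysis and per-protocol sets, and adds: "Analyses will not be repeated between different analysis populations if they only differ by 10% patients", in which case the largest set is used. The deviation table in SAP section 8 leaves it case by case whether a patient with missing biomarker values is excluded from the per-protocol set.

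**The concern.** A rule that is conservative for one analysis need not be so for another. In the responder count, missing = baseline simply means non-response. In an estimate of change, it adds patients who are asserted to have changed by exactly zero. In a correlation between the changes of two markers, a patient with no post-treatment tissue is zero on both axes. When the other patients show reductions, those shared zeros sit together at one end of both scales and produce a positive correlation that the tumours did not show.

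Correlating drug-induced changes with other biomarkers is a listed secondary objective (SAP 4.1). Its p-values feed the false discovery rate step, which presumes valid p-values. At stake are spurious links between markers and change estimates that are too small, with intervals that miss the true change too often.

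**Working it through.** **1. The primary rule, for reference.** Inputs from SAP 5.4: 36 patients, 5 responders needed, 5% chance response per patient, 35% target rate.

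- P(X ≥ 5 | n = 36, p = 0.05) = 0.0324, which agrees with the stated 3.3% per biomarker.
- P(X ≥ 5 | n = 36, p = 0.35) = 0.999. The SAP states 95%; that mismatch is a separate matter and does not affect this point.
- With m patients counted as non-responders, n becomes 36 − m. For m = 3 the type I error is 2.3% and power 99.7%; for m = 6 they are 1.6% and 99.2%. The rule is conservative here.

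**2. Wilcoxon.** If zero differences are dropped, the imputed patients leave the test and the p-value equals the one from observed pairs. It was identical in every simulated data set, with type I error of 4.2% to 4.4%. If zeros are kept in the ranking (Pratt), the type I error is 4.0% to 4.3% and power slightly lower.

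**3. Assumptions for the secondary analyses.** The documents give neither a missing rate nor an effect size on this scale. Assumed: N = 36; two independent markers; log-scale change normal with mean δ and SD 1 in baseline-SD units (pre/post correlation 0.5, since 2 × (1 − 0.5) = 1); m patients missing at random, the same patients for both markers.

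**4. Why the correlation moves.** With missing fraction π = m/36, the ordinary (Pearson) correlation created by shared zeros is πδ² / (1 + πδ²).

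- m = 6, δ = −1: 0.167 / 1.167 = 0.14.
- m = 3, δ = −1: 0.083 / 1.083 = 0.08.
- δ = 0: zero.

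At δ = 0 there is still mild inflation, because the test counts 36 patients when 36 − m carry information. For m = 6 the critical value is in effect 1.96 × √(29/35) = 1.78, a two-sided error of about 7%.

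**5. Simulation (10,000 runs per row; Spearman at two-sided 5%; t interval for the mean).** The mean column is (36 − m)/36 × δ.

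| m | δ | False positives | Mean rho | Mean change | Median change | 95% coverage (mean) |
|---|---|---|---|---|---|---|
| 3 | 0 | 5.8% | 0.00 | 0.00 | 0.00 | 95% |
| 3 | −0.5 | 5.5% | 0.03 | −0.46 | −0.39 | 95% |
| 3 | −1 | 8.4% | 0.11 | −0.92 | −0.89 | 93% |
| 6 | 0 | 7.0% | 0.00 | 0.00 | 0.00 | 95% |
| 6 | −0.5 | 7.9% | 0.06 | −0.42 | −0.27 | 92% |
| 6 | −1 | 20.6% | 0.19 | −0.83 | −0.75 | 84% |

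Other runs of the m = 6, δ = −1 case gave 18.6% to 21% false positives and coverage up to 85%. Observed pairs alone gave 4.6% to 5.2% false positives and 95% coverage throughout.

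**6. Range.** With 4, 7 or 11 missing at δ = −1, false positives were 10%, 25% and 44%, and coverage 90%, 81% and 53% (1,000 runs each).

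**7. What the agreement rule does.** Ten per cent of 36 is 3.6, so with up to 3 patients' difference (3/36 = 8.3%) the second population may be skipped and the larger, imputed set stands alone. With 6 (16.7%) both sets are analysed. If the per-protocol set then excludes all six, requiring significance in both cuts false positives at δ = −1 to about 2.6%. If the case-by-case decision keeps them, there is no such protection.

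**The case against.** The strongest reply is that the plan already contains the remedy. SAP 7.2 points secondary variables to evaluable patients and names non-evaluability for biomarkers as an example of a per-protocol exclusion, and SAP 7.6 demands agreement across populations. Where the per-protocol set does exclude the missing patients and differs from the full set by more than 10%, the agreement rule controls false declarations well. That stands. But the evaluable-patient sentence is not reconciled with 7.6, which imputes without exception, and the other two conditions are not assured. Agreement between sets also governs only what is declared positive; it does not correct the estimates and intervals reported.

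The reply can add that the large figures need a strong effect and shared missingness. This also stands. With different patients missing for each marker, false positives at −1 SD with 6 missing are about 5% to 6%. Correlations of post-treatment levels, rather than changes, gave 5.0%, 5.5% and 10.5% at 0, −0.5 and −1 SD. The plasma-exposure correlations of SAP 7.5 are largely outside the point, because section 8 excludes patients with missing biomarker or PK values from the PKD population.

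A reader might infer that the Wilcoxon p-values are wrong. They are not: with zeros dropped they are the complete-case values. Nor does 7.6 claim conservatism for correlations, since its wording refers to detecting a pre/post change. For that aim, shrinking the estimate does go in the stated direction, although the interval then under-covers.

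**Conclusion.** The point holds in limited form and should be corrected. The imputation is sound for the primary responder count and harmless to the Wilcoxon test. Applied to the full analysis set, it biases mean and median changes towards zero, lowers interval coverage when there is an effect, and makes tests of correlation between changes anti-conservative.

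Under the stated assumptions the harm is small at no effect or −0.5 SD (about 6% to 8% false positives with 3 or 6 missing). At −1 SD it is moderate with 3 missing (about 8%, coverage 92% to 93%) and material with 6 (19% to 21%, coverage 84% to 85%). The last false-positive figure applies where the per-protocol analysis does not exclude the imputed patients, or where the full-set result is read on its own. All sizes depend on a missing rate that the documents do not give. Nothing here supports a conclusion that the primary analysis is compromised.

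**What to change.** Amend the SAP wording in four places:

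- In 7.6, limit missing = baseline to the responder count.
- In 7.1 and 7.3, state that change estimates, their intervals and correlations of changes use patients with both values observed, with N shown for each. State how the Wilcoxon test handles zeros.
- Reconcile 7.6 with the evaluable-patient sentence in 7.2, so that one rule governs secondary variables.
- Confine the statement that the imputation is conservative to the responder analysis.

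No new data are needed. The cost is a slightly smaller N in the secondary analyses, which then rely on the observed patients being representative of those treated. Reporting the number and reasons for missing post-treatment tissue would let readers judge that.

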4 OBJECTIVES AND ENDPOINTS

4.1 Study objectives

Primary Objective: The primary objective of this study is to identify anti-tumor biological efficacy by measuring, in human tumor samples, biomarker changes associated with short exposure to AZD2281 as potential predictors of activity in endometrial carcinoma (EC). This is an exploratory study with a biological primary endpoint.

Secondary objectives:

- To estimate the tolerability to AZD2281 throughout the study and up to 28 days after the last dose of AZD2281.
- To correlate changes induced by AZD2281 with the different type of endometrial carcinoma and other tumor biomarkers (NFkBp65 and p50, PARP, PARP-1, pHistone 2AX, pHistoneH3, VEGF (Vascular Endothelial Growth Factor), HIF(Hypoxia inducible factor)-1alpha).
- To estimate the predictive potential with regard to the following biomarkers (immunostaining for PTEN (phosphatase and tensin homolog), MLH-1 (mutL homolog 1), MSH-2 (mutS homolog 2), MSH-6 (mutS homolog 6), PMS-2 (Postmeiotic Segregation Increased S. Cerevisiae. 2).

- To estimate the potential predictive role of microsatellite instability (MSI) and PTEN loss in clinical tumor changes and PARP inhibition.
- To correlate clinical tumor changes with several targets of PARP inhibition.
- To further explore the use of Pharmacokinetic-dynamic modeling (PBMC modeling) as surrogate pharmacodynamic marker of AZD2281 activity in endometrial tumors.
- To establish a pharmacokinetic-dynamic modeling, based on the status of the variables of time (t), concentration (C) in blood, and molecular effect (E). PK-PD analysis will be performed based on the plasma concentration - PARP inhibition % in the tissue.

Secondary initial objectives that were dismissed:

- To quantify AZD2281 levels in human tissues after the oral administration of the drug.
- To explore the correlation between intratumoral AZD2281 concentrations with plasma PK parameters and molecular alterations in EC after AZD2281 treatment.
- To compare intratumoral AZD2281 concentrations with those present in healthy tissues.
- To establish a pharmacokinetic-pharmacodynamic modeling, based on the status of the variables of time (t) and concentration (C) in the tissue.

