Significant inhibition of biomarker activity will be declared if 5 of 36 patients have significant inhibition at patient level. Based on these assumptions, there is a 95% power to detect a true 35% rate of significant inhibition with an overall alpha error below 10%. As we consider three biomarkers in the primary analysis (cyclin D1, Ki67 and active caspase 3), the type I error was divided into 3,3% (<5%) for each analysis. Power and type I error has been derived from the binomial distribution (Rubinstein et al 2010), according to (A'Hern 2001).

Study dropouts

We assume the loss of patients between recruitment and end of study. Study dropouts will be analyzed as patients not displaying significant inhibition of the biomarker activity.

5.5 Randomization and blinding.

(ICH E3; 9.4.3, 9.4.6. ICH E9; 2.3.1, 2.3.2)

The randomization or blinding was not planned in this study.

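### Coding an untested mutation, MSI, PTEN or MMR marker as absent misclassifies patients, understates prevalence and dilutes the marker contrasts; a false contrast can arise only if marker and post-treatment value are missing together

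*SAP*

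**What the plan says.** SAP 7.6 has three imputation rules that meet in the marker analyses.

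- Missing qualitative result: "the lack of mutation or the characteristic analyzed will be assumed".
- Missing post-treatment value: "Patients without quantitative values at the follow-up visits will be assigned the same value as in the baseline visit". The change is then zero.
- Missing baseline value: "Patients without quantitative biomarker values at the baseline visit will be assigned the mean of the patients at that visit". If the follow-up value is missing as well, the change is again zero.

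The SAP's remark that imputation is conservative comes before the qualitative rule and concerns detecting a pre/post change. No rationale is given for the qualitative rule. Section 7.6 then adds that an analysis counts as positive only if its result is equivalent in every population used.

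The rule reaches planned analyses. SAP 4.1 lists as a secondary objective "To estimate the potential predictive role of microsatellite instability (MSI) and PTEN loss in clinical tumor changes and PARP inhibition". SAP 7.3 compares biomarker levels and pre/post differences between molecular subsets by Mann-Whitney. Figure 4 in SAP 9.1 shows biomarker change by mutation or deficiency, MSI included, in both the full analysis and per-protocol sets.

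On secondary variables, the per-protocol paragraph of SAP 7.2 says that "the number of evaluable patients for a certain biomarker analysis set will be considered".

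**The concern.** No result is not a negative result. Among untested patients, those who truly carry the marker are moved into the comparison group. This understates prevalence and pulls the two groups together, so the MSI and PTEN objective loses sensitivity.

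A second effect runs the other way. A patient with neither a marker result nor a post-treatment value is entered as negative with no change. If the drug lowers the biomarker, such patients weaken the apparent effect in the negative group only, and marker-positive tumours look more responsive without any true difference. An imputation that is cautious for a pre/post comparison need not be cautious for a comparison between marker groups.

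**Working it through.** **The plan's own figures.** The SAP gives no figure for missing markers or for the predictive analyses. Its only design figures belong to the primary rule of 5 responders in 36. With a 5% patient-level error, P(X ≥ 5 | 36, 0.05) = 3.24% per biomarker, and 3 × 3.24% = 9.7%, in line with the stated 3.3% each and under 10% overall. Power at a 35% rate comes to 99.9%, above the stated 95%. That rule does not use marker status, so none of this bears on the point.

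**Inputs.** From the SAP: N = 36, the 7.6 rules, Mann-Whitney. Assumed, because the documents give no values: marker prevalence, effect size and number missing. The tests below are two-sided at 5%.

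**1. Marker alone missing, at random.** Take prevalence p = 0.40, fraction missing q, and a true difference of 1 SD.

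- Apparent prevalence = p(1 − q).
- Apparent difference = (1 − p) / [(1 − p) + pq], because the coded-negative group now contains a share pq of true positives.

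| Missing of 36 | Apparent prevalence | Apparent difference |
|---|---|---|
| 4 | 0.40 × 32/36 = 35.6% | 0.60/0.644 = 0.93 SD |
| 7 | 0.40 × 29/36 = 32.2% | 0.60/0.678 = 0.89 SD |
| 11 | 0.40 × 25/36 = 27.8% | 0.60/0.722 = 0.83 SD |

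Simulation agrees, at about 0.93 to 0.82 SD over the same range. Power is 68%, 61% and 51% under the SAP rule, against 72%, 66% and 59% if the untested patients are simply omitted. The imputation therefore loses more power than exclusion does.

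**2. Marker and post-treatment value missing in the same patients, no true marker effect.** Let both groups change by −1 SD, with p = 0.40 and m patients missing both. The coded-negative group holds 0.60(36 − m) observed patients and m zeros, so the spurious difference is m / [0.60(36 − m) + m] SD.

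- m = 3: 3/(19.8 + 3) = 0.13 SD. Simulated false-positive rate 5.8%.
- m = 6: 6/(18 + 6) = 0.25 SD. Simulated false-positive rate 11.8%.
- Patients with observed data only: 5.0-5.2%.

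A wider grid (prevalence 30% or 50%, geometric mean reduction 33% or 50%, SD of log change 0.5 or 0.7) gave 5-8% with 3 patients, 9-20% with 6 and 14-40% with 9. Analysing only patients with both values observed gave 4-5% throughout. If only the marker, only the post-treatment value, or each independently was missing, the rate stayed at 4-6%.

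**3. The agreement rule in 7.6.** In the setting of step 2 with m = 6, a separate run gave 12.0% for the imputed set alone. Requiring significance also in a set that drops those six patients brought this to 2.7%. With a change of −0.5 SD the figures were 8.9% and 3.5%; with −1.5 SD, 14.7% and 2.4%.

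**4. Whether those patients do leave the per-protocol set.**

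- SAP 7.2 gives patients not evaluable for biomarkers as an example of a per-protocol exclusion.
- The SAP 8 table leaves exclusion for missing or non-evaluable biomarker values to individual judgement.
- The same table does not exclude a patient whose pre-treatment biopsy was never collected.
- SAP 7.2 drops the repeat analysis, and uses the largest set, when the sets differ by only 10% of patients. Since 3/36 = 8.3% and 4/36 = 11.1%, the check falls away at about 3 patients.

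**The case against.** The strongest reply is the agreement rule in 7.6. A reader might take 12% as the plan's false-positive rate; the documents do not support that, because significance in the imputed set alone is not the SAP's criterion. If the per-protocol set drops the affected patients, step 3 puts the rate below 5%. The 10% rule removes the check only near 3 patients, where the inflation is about 6% against 5%. This stands, on condition that those patients are in fact dropped, which the SAP 8 table does not secure.

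A reader might also infer that the rule is bound to create a false predictive effect. It is not: that needs marker and post-treatment value missing in the same patients. Inclusion criterion 1 requires an adequate, centrally checked diagnostic biopsy, with re-biopsy if needed, so a patient who misses surgery would normally still have tissue for testing. On the other side, the SAP does not say which specimen supplies each marker, and pre-treatment frozen tissue is only recommended where possible. Joint missingness is plausible but not shown to be likely.

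Nor is a flat contradiction between 7.2 and 7.6 shown. The evaluable-patients sentence sits in the per-protocol paragraph, so imputation in the full set and evaluable patients in the per-protocol set is a natural reading. The SAP does not say so, which makes this a matter for reconciliation.

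Two further limits stand. The SAP does not claim that its qualitative rule is conservative. And for PTEN and MMR staining it does not define whether the characteristic is loss or expression, so it is not settled which group receives the untested patients.

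None of this answers the misclassification. The agreement rule corrects neither the prevalence in the full set nor the dilution.

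**Conclusion.** The concern holds for misclassification and dilution, and conditionally for a false contrast. As written, 7.6 biases prevalence downward in the full analysis set and shrinks a true 1 SD marker difference to about 0.93-0.82 SD with roughly 10-30% of markers missing, assuming 40% prevalence and random missingness. That is a modest loss, but excluding the same patients would lose less power.

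Inflation of the false-positive rate in the imputed set, to about 6% with 3 and 12% with 6 of 36, rests on joint missingness, 40% prevalence and a change of −1 SD in both groups. The SAP's safeguard can contain it but is not guaranteed to operate.

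The affected analyses are secondary and exploratory; the primary 5-of-36 rule is untouched. The SAP should be changed before the marker analyses are run.

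**What to change.** - In 7.6, code a missing qualitative marker as not evaluable.
- Run marker contrasts in patients with an observed marker and an observed change.
- Leave not-evaluable patients out of prevalence denominators and report their number for each marker.
- Keep the assume-absent rule only as a labelled sensitivity analysis.
- Align 7.2 with 7.6 by stating which patients enter the subset tests and Figure 4 in each population.
- For PTEN and MMR staining, define which result counts as having the characteristic.

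The cost is SAP wording and a slightly smaller denominator per marker. No new data are needed.
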